9.14. Concomitant Medications/Procedures

At screening, information on prior and concomitant medications taken within the previous 30 days (whether continuing or not) will be collected. All prior and concomitant medications, including pre- and post-ocular procedure medications, will be listed in the subject's medical record and on the concomitant medication eCRF page. At each study visit, each subject should

be questioned concerning any new medications or changes in the subject's current medications since the previous study visit.

For all medications, the generic name, indication, route of administration, frequency, dose, start date and stop date (if applicable) will be collected.

9.15. Description of Procedures

Refer to Table 2 and the appendices (Section 18, Section 19 and Section 20) for details about the following procedures.

9.15.1. Slit Lamp Examination

Slit lamp examination should be performed using the Investigator's standard procedure. This procedure should be the same for all subjects examined at the site and use the same equipment. Observations should be made to indicate the absence or presence of findings for conjunctiva, cornea, iris, and anterior and posterior chambers. All findings are to be documented in the source documentation and the appropriate eCRF.

9.15.2. Dilated Indirect Ophthalmoscopy

Dilated indirect ophthalmoscopy should be performed as part of each ophthalmic examination. This procedure should be the same for all subjects examined at the site and use the same equipment. All findings are to be documented in the source documentation and the appropriate eCRF.

9.15.3. Visual Acuity

BCVA will be measured according to the standard procedure developed for ETDRS at 4 meters (or at 3 meters if the electronic ETDRS system is employed). Corrected-distance VA is to be reported as number of letters read correctly by the subject. The details of refraction and VA determination procedures are provided in Section 18.

9.15.4. Intraocular Pressure

IOP will be reported as an average of 3 measurements (preferably using Goldmann applanation tonometry), using the Investigator's standard procedure.

9.16. Laboratory Testing

Clinical laboratory testing will include HIV and syphilis serology testing, and urine pregnancy tests (for females of childbearing potential).

9.17. **Protocol Deviations**

The Investigator will not deviate from the requirements from this protocol without prior approval from pSivida Corp. unless necessitated by a medical emergency (i.e., those that impact subject safety or the validity of the study). All other significant changes to the protocol will be made by pSivida Corp. as a protocol amendment and approved by IRB/EC and the appropriate regulatory authority prior to implementation.

9.18. Study Termination or Suspension

If the trial is prematurely terminated or suspended for any reason, the Investigator/institution should promptly inform the trial subjects, should assure appropriate therapy and follow-up for the subjects, and, where required by the applicable regulatory requirement(s), should inform the regulatory authority.

In addition, if the Investigator terminates or suspends a trial without prior agreement of pSivida, the Investigator should inform the institution where applicable, and the Investigator/institution should promptly inform pSivida and the IRB/EC, and should provide pSivida and the IRB/EC a detailed written explanation of the termination or suspension.

If pSivida terminates or suspends this trial, the Investigator should promptly inform the institution where applicable and the Investigator/institution should promptly inform the IRB/EC and provide the IRB/EC a detailed written explanation of the termination or suspension.

If the IRB/EC terminates or suspends its approval/favorable opinion of this trial, the Investigator should inform the institution where applicable and the Investigator/institution should promptly notify pSivida and provide pSivida with a detailed written explanation of the termination or suspension.

10. INVESTIGATIONAL MATERIALS

10.1. FAI Insert

The FAI insert is an injectable intravitreal sustained-release FA delivery system pre-loaded into an injection device. Each insert contains a drug core of FA as the active ingredient within a cylindrical polyimide polymer tube 3.5 mm long with an external diameter of 0.37 mm. One end of the tube is capped with an impermeable polymer (silicone adhesive); the other end is capped with a permeable polyvinyl alcohol membrane. FA release occurs through the permeable end of the cylinder. Each FAI insert contains 0.18 mg FA and delivers FA into the vitreous humor for 36 months, as demonstrated in a clinical pharmacokinetics study of Iluvien (Campochiaro 2013). In vitro data demonstrate that initial FA release occurs at a rate of approximately 0.2 μ g FA/day, gradually decreasing over three years to a rate of approximately 0.1 μ g FA/day. The FAI insert is designed to be injected through the pars plana into the vitreous.

10.2. FAI Insert in Mk I Inserter

The FAI insert in the Mk I inserter will be supplied as an individual finished product in primary, secondary and tertiary packaging. The primary packaging is the applicator, which includes a 25 gauge needle that is attached to the applicator. The FAI insert is pre-loaded in the applicator. The pre-loaded applicator is placed into the secondary packaging, a 2.5" x 15" foil chevron pouch and heat-sealed. Lastly, the foil pouch is placed into a 3.5" x 18" Tyvek chevron pouch. The outer chevron pouch will be labeled as investigational drug in accordance with applicable regulations. The assembled units are subsequently sterilized by gamma irradiation, resulting in a sterile, single-use product. Each unit is placed in a SBS shelf carton for shipment.

Fluocinolone Acetonide Intravitreal Insert Protocol PSV-FAI-006 [Version 3.0; April 4, 2016]

10.3. FAI Insert in Mk II Inserter

The FAI insert in the Mk II inserter will be supplied as an individual finished product in primary, secondary and tertiary packaging. The primary packaging is the applicator, which includes a 27 gauge needle that is attached to the applicator. The FAI insert is pre-loaded in the applicator, which is then placed in a tray with cover. This assembly is then placed into the secondary packaging, a 6" x 14.3" foil chevron pouch and heat-sealed. Lastly, the foil pouch is placed into a 7.5" x 18" Tyvek chevron pouch. The outer chevron pouch will be labeled as investigational drug in accordance with applicable regulations. The assembled units are subsequently sterilized by gamma irradiation, resulting in a sterile, single-use product. Each unit is placed in a SBS shelf carton for shipment.

10.4. Investigational Product Storage

Investigational product must be stored at controlled room temperature [15°-25°C (59-77°F)] in a secured location accessible only to study personnel.

10.5. Supply and Accountability of Investigational Materials

pSivida Corp. will supply the finished product units (Mk I inserter or Mk II inserter) for this study. A log will be maintained at each study site, showing the subject/eye ID number for which each unit is dispensed, the date and who dispensed the unit. Sufficient finished product units will be supplied to each investigative site to allow replacement, as necessary, of any damaged unit.

The Investigator must maintain records of all shipments of study materials and account for all used and unused materials. All unused and damaged study materials must be returned to pSivida Corp. or destroyed on site, with an accounting of all materials supplied, used, and returned, and an explanation for any discrepancies.

11. ASSESSMENT OF SAFETY

11.1. Adverse and Serious Adverse Events

The following are specific definitions of terms guided by the International Conference on Harmonization (ICH) Guidelines for Good Clinical Practice (GCP) and the U.S. Code of Federal Regulations (CFR) that apply to this section.

11.1.1. Adverse Event

An adverse event (AE) is defined as any new untoward medical occurrence or worsening of a pre-existing medical condition in a patient or clinical investigation subject administered an investigational (medicinal) product; an AE does not necessarily have a causal relationship with this treatment. An AE can therefore be any unfavorable and unintended sign (including an abnormal laboratory finding, for example), symptom, or disease temporally associated with the use of investigational product, whether or not considered related to the investigational product.

11.1.2. Serious Adverse Event

A serious adverse event (SAE) is any untoward medical occurrence that:

- Results in death
- Is life-threatening

(The term "life-threatening" refers to an event in which the subject was at risk of death at the time of the event; it does not refer to an event which hypothetically might have caused death if it were more intense.)

- Requires in-patient hospitalization or prolongs existing hospitalization
- Results in persistent or significant disability / incapacity
- Is a congenital anomaly / birth defect
- Is a medically important event or reaction (Medical and scientific judgment should be exercised in deciding whether other situations should be considered serious such as important medical events that might not be immediately life-threatening or result in death or hospitalization but might jeopardize the patient or might require intervention to prevent one of the other outcomes listed in the definition above.)

The following hospitalizations are not considered SAEs:

- A visit to the emergency room or other hospital department < 24 hours, that does not result in admission (unless considered "important medical event" or life threatening event)
- Elective surgery, planned prior to signing consent
- Admissions as per protocol for a planned medical/surgical procedure

- Routine health assessment requiring admission for baseline/trending of health status (e.g., routine colonoscopy)
- Medical/surgical admission for purpose other than remedying ill health state and was planned prior to entry into the study. Appropriate documentation is required in these cases
- Admission encountered for another life circumstance that carries no bearing on health status and requires no medical/surgical intervention (e.g., lack of housing, economic inadequacy, care-giver respite, family circumstances, administrative)

11.1.3. Protocol-Defined Ocular Adverse Events

The following ocular events must be reported as AEs during this trial:

- decrease in visual acuity of ≥ 15 letters, compared to the most recent previous measurement of visual acuity
- moderate or severe (grade 3 or 4) ocular findings compared to the last ophthalmic examination
- worsening of ≥ 2 steps in anterior chamber cell count or vitreous haze, compared to the last ophthalmic examination
- increase in IOP of \geq 10 mmHg at two visits at least 1 week apart or an increase in IOP to \geq 25 mmHg

11.1.4. Protocol-Defined Ocular Serious Adverse Events

The following ocular events must be reported as SAEs during this trial:

- An AE which causes a decrease in visual acuity of \geq 30 letters, compared to the most recent previous measurement of visual acuity, lasting more than 1 hour
- An AE which causes a decrease in visual acuity to light perception or worse, lasting more than 1 hour
- An AE which requires surgical intervention (e.g., conventional surgery, vitreous tap or biopsy with intravitreal injection of anti-infectives, or laser or retinal cryopexy with gas) to prevent permanent loss of sight
- An AE which is associated with severe intraocular inflammation (i.e., 4.0 anterior chamber cell score, 4+ flare or 4+ vitritis)
- Two consecutive IOP measurements of 30 mmHg or higher taken at least 72 hours apart when a subject is already being treated with two glaucoma medications
- An IOP < 6 mmHg requiring medical intervention
- An AE which in the opinion of the Investigator requires medical or surgical intervention to prevent permanent loss of sight

11.1.5. Laboratory Test Abnormalities

All laboratory test values captured as part of the study should be recorded on the appropriate laboratory test results pages of the eCRF.

In addition, the following laboratory abnormalities should also be captured on the non-serious AE CRF page (paper or electronic) or SAE paper CRF page as appropriate:

- Any laboratory test result that is clinically significant or meets the definition of an SAE
- Any laboratory abnormality that required the subject to receive specific corrective therapy

It is expected that, wherever possible, the clinical rather than the laboratory term would be used by the reporting Investigator (e.g., anemia versus low hemoglobin value).

11.1.5.1. Pregnancy

Sexually active women of child bearing potential (WOCBP) must be encouraged to use an effective method of birth control during the course of the study, in a manner such that risk of failure is minimized.

All WOCBP MUST have a negative urine pregnancy test within 48 hours prior to receiving the investigational product. If the pregnancy test is positive, the subject must not receive the investigational product and must not be enrolled in the study.

Pregnancy testing must also be performed on all WOCBP throughout the study as specified and the results of all pregnancy tests (positive or negative) recorded on the eCRF.

Any female subject of child-bearing potential should be instructed to contact the Investigator immediately if the subject suspects that she may be pregnant (e.g., missed or late menstrual period) at any time during study participation. NOTE: Pregnancy is not classified as an adverse event in this trial.

11.2. Adverse Event Assessment

11.2.1. Relationship to Study Treatment

The study treatment relationship to each AE should be determined by the Investigator using these explanations:

Unrelated: Evidence indicates no plausible direct relationship to the study medication, device or procedure, or there is a reasonable causal relationship between non-investigational product, concurrent disease, or circumstance and the AE.

Possibly Related: There is reasonable causal relationship between the investigational product, device or procedure and the AE suggests that the association of the event with the study medication, device, or procedure is unknown; however, the adverse event is not reasonably supported by other conditions.

Probably Related: Suggests that a reasonable temporal sequence of the event with medication administration, device usage or the index procedure exists and, based upon the

Investigator's clinical experience, the association of the event with study medication, device or procedure is likely.

The Investigator will make the determination of relationship to the investigational product for each AE (Unrelated, Possibly Related or Probably Related). The Investigator should decide whether, in his or her medical judgment, there is a reasonable possibility that the event may have been caused by the investigational product, device or procedure. If no valid reason exists for suggesting a relationship, then the AE should be classified as "unrelated".

If there is any valid reason, even if undetermined, for suspecting a possible cause-and-effect relationship between the investigational product and the occurrence of the AE, then the AE should be considered as related.

If the relationship between the AE/SAE and the investigational product is determined to be "possible" or "probable" the event will be considered to be related to the investigational product for the purposes of expedited regulatory reporting.

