5.1. Uveitis

Uveitis is defined as inflammation of the uveal tract (iris, ciliary body, choroids) or adjacent structures. The cause of inflammatory reaction of the inner eye can be infectious, traumatic, neoplastic or autoimmune. According to the classification scheme recommended by the International Uveitis Study Group, the disease can be classified on the basis of anatomic locations: anterior, intermediate, posterior, or panuveitis.

Uveitis has been estimated to be responsible for approximately 10% of blindness in the United States (Suttorp-Schulten 1996). Generally, posterior uveitis occurs in all age groups and affects people of different ethnic origins. The inflammation that affects the choroid and retina may be a primary intra-ocular process or may be an ocular manifestation of systemic disease. Posterior uveitis accounts for most of the loss of vision in eyes with uveitis, due to any one or more of the following: cystoid macular edema, choroidal neovascularization, glaucoma, retinal detachment, subretinal fibrosis, cataract, or optic disk atrophy.

A product that is relatively simple to administer and delivers corticosteroid locally for an extended period of time may offer significant benefits over existing local and systemic steroid therapies.

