5.2.2.3. Previous Human Experience with the FAI insert in uveitis subjects

The FAI insert is currently being evaluated in two phase 3 trials (PSV-FAI-001 and PSV-FAI-005) in subjects with chronic non-infectious uveitis affecting the posterior segment. In both studies, subjects are randomized (2:1) to receive either an intravitreal administration of the FAI insert or sham injection, respectively. Following treatment, subjects are being followed for three years. As of August 1, 2015, PSV-FAI-001 has completed enrollment (N=129) and is following subjects, and PSV-FAI-005 is actively enrolling subjects.

All study data are currently masked to treatment assignment. As of August 1, 2015, a total of 42 serious adverse events (SAEs) have been reported from both studies; none of these events was considered to be a suspected unexpected serious adverse reaction (SUSAR) that requires expedited safety reporting. Eight of the 42 SAE reports were non-ocular events judged by the investigator to be unrelated to study treatment. The remaining 34 SAE reports involved ocular events, of which 17 events were reported in the non-study eye and judged by the investigator to be unrelated to study treatment. The remaining 17 ocular events were reported in the study eye: 9 events were assessed by the investigator as not related to study treatment [sterile endophthalmitis (two events), uveitis (two events), macular edema (two events), cataract worsening, neovascular glaucoma, optic disc swelling], and 8 events were assessed by the investigator as possibly or probably related to study treatment [elevated IOP (three events), cataract (two events), hypotony (two events), and cystoid macular edema]. Additional information may be found in the IB.

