5.2.3. Current benefit-risk profile of the FAI insert

Because the efficacy and safety of the FAI insert in uveitis subjects have not yet been fully evaluated, the current benefit-risk profile is based primarily upon previous human experience with Retisert and Iluvien, as well as the (masked) experience to date in PSV-FAI-001. Currently, all data are consistent with the expected benefit-risk profile of the FAI insert; subjects are expected to experience a significant decrease in the frequency of recurrence of uveitis, and are expected to most frequently experience an adverse event associated with cataract or elevated IOP.

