11.3. Recording of Adverse Events

Medical conditions or diseases present before a subject starts study treatment are only considered AEs if they worsen after the start of the study treatment.

Adverse events can be spontaneously reported or elicited at each study visit through open-ended questioning, examination or evaluation of a subject. In order to prevent reporting bias, subjects should not be questioned regarding the specific occurrence of one or more AEs.

The Investigator will record all AEs of enrolled subjects in the appropriate eCRF. If known, the diagnosis of the underlying illness or disorder should be recorded, rather than its individual symptoms.

The following information should be captured for all AEs: onset and end date, severity, seriousness, relationship to investigational product, action taken, treatment required and outcome. If treatment for the AE was administered, it should be recorded on the appropriate eCRF page.

Completion of supplemental eCRF pages may be requested for AEs and/or laboratory abnormalities that are reported / identified during the course of the study.

The Investigator will take or organize all appropriate and necessary therapeutic measures required for resolution of the adverse event. Any medication necessary for the treatment of an adverse event must be recorded on the concomitant medication eCRF. If more than one distinct AE occurs, each event should be recorded separately.

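### Protocol 11.2.1 gives conflicting causality rules for an adverse event that both the insert and another cause could explain, so the treatment-related summaries depend on which sentence the investigator applied

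*Protocol*

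**What the plan says.** Protocol 11.2.1 defines three ratings and then adds general instructions.

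- **Unrelated** has two limbs joined by *or*. One is the absence of a plausible direct relationship. The other is that "there is a reasonable causal relationship between non-investigational product, concurrent disease, or circumstance and the AE".
- **Possibly Related** describes a reasonable causal link whose association is unknown, and adds: "however, the adverse event is not reasonably supported by other conditions".
- **Probably Related** asks for a reasonable temporal sequence and a likely association. It does not require that other causes be absent.
- **General instructions.** "If no valid reason exists for suggesting a relationship, then the AE should be classified as" unrelated. Conversely, "If there is any valid reason, even if undetermined, for suspecting a possible cause-and-effect relationship between the investigational product" and the event, it should be considered related.

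SAP 9.1.2 takes the investigator's rating as given and repeats the three labels. SAP 9.1.3 counts Possibly and Probably together as related. The rating feeds the overview of treatment-related and treatment-related serious TEAEs (SAP 9.1), the relationship table (SAP 9.1.2) and the related-by-severity tables (SAP 9.1.3, Protocol 14.3.6).

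On the likely events, Protocol 5.2.3 says that subjects "are expected to most frequently experience an adverse event associated with cataract or elevated IOP". Protocol 5.1 attributes vision loss in uveitic eyes to "cystoid macular edema, choroidal neovascularization, glaucoma, retinal detachment, subretinal fibrosis, cataract, or optic disk atrophy".

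**The concern.** A causality table is readable only if two investigators with the same facts would be directed to the same rating. Here they are not. With a new cataract in a treated uveitic eye, one investigator can apply the second limb of Unrelated and another can apply the any-valid-reason instruction, and both follow the protocol. The overlap falls on the event types for which a reader of a 12-month steroid insert study most wants an attribution. Insert safety over 12 months is the secondary objective. With at least 10 investigators and about 30 eyes, each rates about three eyes (30/10), which leaves little room for different readings to average out.

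**Working it through.** The plan gives no figure on this point to reproduce, so the check is mainly of the text.

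**Step 1. Apply each statement in Protocol 11.2.1 to an event with two reasonable causes, the insert and another.**

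| Statement | Insert is a likely cause | Insert is a real possibility, but not likely |
|---|---|---|
| Unrelated, alternative-cause limb | met | met |
| Possibly Related | barred by the other cause | barred by the other cause |
| Probably Related | met | not met |
| Instruction: unrelated if no valid reason | not met | not met |
| Instruction: related if any valid reason | met | met |

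In the middle column the event satisfies both Unrelated and Probably Related. In the right-hand column the instruction requires *related*, but neither related category fits and only Unrelated does. The section states no order of precedence. If there is no reasonable competing cause, the alternative-cause limb is not met and the conflict disappears.

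**Step 2. Can such events occur here?** Every treated eye receives the insert, and Protocol 5.2.3 names cataract and elevated IOP as the adverse events most expected with it. That is a valid reason to suspect the product. Every study eye has a history of posterior-segment uveitis (Protocol 8.1), and Protocol 5.1 names cataract and glaucoma among the causes of vision loss in such eyes. SAP 9.1.8 counts glaucoma terms as IOP elevations. Recurrences are treated by the investigator's usual practice (Protocol 9.11), and systemic steroids for uveitis are not prohibited (SAP 7.1). Some events, though not all, will therefore meet both rules.

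**Step 3. Does anything later resolve it?** SAP 9.1.2 handles only a missing rating, which it counts as Probably Related. SAP 9.1.3 only pools categories. The one relationship review, in SAP 9.1.9, covers onset within 7 days and the injection procedure. The fields required for every adverse event (Protocol 11.3) are "onset and end date, severity, seriousness, relationship to investigational product, action taken, treatment required and outcome"; none records an alternative cause or the rule used.

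**Step 4. Size.** Let N be the number of treated eyes, *a* the eyes with an event that is related under either rule, and *x* the further eyes whose only candidate event has two reasonable causes. The related rate is a/N if the alternative-cause limb is always applied and (a + x)/N if the any-valid-reason instruction is always applied. The gap is x/N.

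- Per affected eye, using the planned numbers: 1/30 = 3.3 percentage points pooled, 1/20 = 5 points for Mk II, 1/10 = 10 points for Mk I.
- The documents do not give *x*. For illustration only, with a = 0 and N = 30, assumed x = 3, 6 or 9 gives 0% against 10%, 20% or 30%. At x = 9 the exact (Clopper-Pearson) 95% intervals are 0% to 11.6% and 14.7% to 49.4%.

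These values show how the rate responds to the rule. They do not forecast it.

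**The case against.** The strongest reply is that the three definitions are only explanations, and that the later paragraph is the operative test: ask whether there is a reasonable possibility of causation and, given any valid reason, rate the event related. Protocol 5.2.3 supplies that reason for cataract and IOP. This is a sensible reading, but the text does not say that it prevails. The investigator must still choose one of three labels, and Possibly Related, although its sentence is garbled, excludes an event that other conditions explain.

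Other parts of the reply stand and limit the point.

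- **Scope.** A reader might infer that every cataract or IOP rating is ambiguous. The documents do not support that. Only a history of uveitis is required. Protocol 8.2 excludes IOP above 21 mmHg and IOP-lowering therapy in the study eye. It also excludes recent local steroid and, unless incisional surgery has stabilised IOP, glaucoma or a known steroid response. A pressure rise 10 to 30 minutes after injection has little competing explanation.
- **Expedited notification.** A reader might infer that safety notices would be missed. Protocol 11.5 requires an SAE to be both suspected and unexpected. Cataract and raised IOP are expected, so the rating matters there only for an unexpected SAE.
- **Evidence of misrating.** In Protocol 5.2.2.3, "8 events were assessed by the investigator as possibly or probably related to study treatment", including three of elevated IOP and two of cataract, while one cataract worsening and one neovascular glaucoma were rated not related. Those trials are masked with a sham arm, and their rating rules are not given. The split does not show that any rating was wrong.
- **Other information.** Medication indications and dates (Protocol 9.14), listings of haze and cells (SAP 9.2.5) and SAE narratives (Protocol 11.4.1) will often reveal a competing cause, though not the rule applied.
- **Comparison of inserters.** Randomization stratified by investigator tends to balance rating habits between arms. It does not settle the pooled level.

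**Conclusion.** The contradiction is in the text, and neither document resolves it. It affects events for which the insert and another cause are both reasonable explanations, and only the outputs built on the rating: the treatment-related and treatment-related serious TEAE summaries, the relationship table and the related-by-severity tables.

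The all-cause TEAE tables, cataract and IOP special-interest tables (SAP 9.1.8), IOP thresholds (SAP 9.2.2), IOP medication (SAP 7.1.3), IOP and cataract surgery (SAP 7.2.1, 7.2.2), the primary endpoint and the success criterion do not use the rating.

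The size is x/N with *x* unknown. It would be tempting to say that the related rate could be anything from zero to the full cataract and IOP rate. Reaching zero would require every event to have a competing cause and every investigator to disregard the any-valid-reason instruction, and nothing in the documents points to that. The conclusion assumes that at least some cataract or IOP events will have a reasonable competing cause, which Protocol 5.1 makes likely but does not quantify. The change is worth making because it is cheap and the present wording can rate a plausibly insert-caused event Unrelated.

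**What to change.** 1. In Protocol 11.2.1, delete the alternative-cause limb of Unrelated. Otherwise, state that an alternative cause does not make an event Unrelated while the insert, inserter or procedure remains a reasonable possibility.
2. Redefine Possibly Related: the product could have contributed, although other causes are also plausible.
3. Cite this rule in SAP 9.1.2, and name the all-cause cataract and IOP tables as the main Month 12 evidence on those events.

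**Cost.** A short protocol amendment, which under Protocol 9.17 needs IRB/EC and regulatory approval, and one SAP sentence. Somewhat more events will be rated Possibly Related.

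**Optional.** An adverse-event field for other plausible causes, a listing of steroid timing, and a query of events already rated Unrelated go beyond what the defect requires. Such a query could only move counts upward, so if it is done, the ratings before and after it should both be reported.
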